8. PHARMACOKINETICS

The PK endpoint is plasma concentrations for NBI-1065846 after a single dose and at steady state.

8.1. Concentrations of NBI-1065846

The plasma concentrations of NBI-1065846 and metabolites, if appropriate will be summarized with descriptive statistics, which will include the coefficient of variation (CV [%]), geometric mean, and geometric CV (%) in addition to the descriptive statistics described in Section 5.1, by sampling time point (predose, 0.5-2 hour, and 2-36 hour) and the study visit based on the PK analysis set. Concentrations below the lower limit of quantification will be set equal to zero for all plasma concentration summaries.

Neurocrine Biosciences, Inc. Statistical Analysis Plan Study NBI-1065846-MDD2020 16August2023

9. SAFETY

The safety objective of the study is to characterize the safety profile of NBI-1065846 as measured by TEAEs and SAEs, vital signs, clinical laboratory tests, ECG, medications, and safety scales. All outputs for safety endpoints will be based on the Safety Analysis Set. The analysis of the safety data will be based on descriptive statistics and presented by treatment group and the study visit unless otherwise noted. Safety data will not be subject to any imputation and will be summarized on an observed case basis. No formal hypothesis-testing analysis of safety data will be performed.

9.1. Study Treatment Dosing and Compliance

The duration of exposure to randomized study treatment will be calculated as: last dose date – first dose date +1.

Duration of exposure will be summarized with descriptive statistics by treatment group.

The percentage of study drug compliance will be defined as (number of tablets dispensed – number of tablets returned) / 8 x 100%.

Assessment of compliance will be summarized as number and percentage of subjects receiving <80%, 80%-120%, and >120% of prescribed study treatment.

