6.2. Study Treatment Administration

Study treatment will be administered orally once weekly (every 7 days \pm 2 days), with each dose taken at least 5 days apart. Subjects receive a loading dose of 160 mg (consisting of four 40 mg tablets) in the clinic on Day 1 (Week 1) and subsequently 80 mg (consisting of two 40 mg tablets) once weekly (Weeks 2 to 8) thereafter. Subjects will also receive their second (Day 8), and fifth (Day 29) doses of study treatment in the clinic. Subjects will take study treatment at home on Days 15, 22, 36, 43, and 50. Study treatment will be administered with 240 mL of water and may be administered with or without food.

If a subject forgets or is unable to take the study treatment, the dose can be taken ± 2 days from the scheduled weekly dose (with each dose taken at least 5 days apart); otherwise the study treatment should be taken at the next dosing time.

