- ^h If a female of childbearing potential has an indeterminant β-hCG pregnancy test result, the test should be repeated during the screening period and the subject discussed with the medical monitor.
- ⁱ Only for postmenopausal women.
- Urine drug screen (UDS) will be analyzed at screening by the central lab. A UDS kit provided by the central laboratory will be used at the site to confirm eligibility on Day 1. Drug/alcohol screening may be repeated at any

time per the investigator's clinical judgment. Any positive UDSs during conduct of the study must be discussed with the Sponsor or designee to determine the subject's disposition.

k A trained rater will read the PCRS to the subject prior to administration of the efficacy rating assessments. After administering the PCRS, the efficacy assessments should be performed in the following order throughout the study: SHAPS (at screening and baseline only), DARS,

MADRS, HAM-D17 (at screening and baseline only), CGI-S,

- .
- ^m If the subject discontinues study treatment, a blood sample for PK is needed at any time during early ET visit.
- ⁿ One bottle will be dispensed to the site at Baseline/Day 1 and will remain in the clinic for onsite subject dosing (ie, on Days 1, 8, and 29). A second bottle will be dispensed to the subject at Day 8 to take home for at-home dosing (ie, on Days 15, 22, 36, 43, and 50).
- Ocllect any remaining study treatment from the subject at Day 57 or ET visit if the subject discontinues study treatment.
- P Each dose of study treatment should be taken at least 5 days apart. Onsite dosing in the clinic will occur on Day 1, Day 8, and Day 29. Subjects should hold morning study treatment dose until instructed to take at the study site in order to collect predose PK blood samples. Subjects will take study treatment at home on Days 15, 22, 36, 43, and 50. At each onsite or virtual study visit (except the Day 1 visit), the investigator or designee will remind subjects to take their study medication on the next scheduled day. For weeks with no study visit scheduled, this reminder should occur via telephone. The subject should also be reminded that if they forget or are unable to take the study treatment, the dose can be taken ± 2 days from the scheduled weekly dose (with each dose taken at least 5 days apart); otherwise the study treatment should be taken at the next dosing time.
- ^q A compliance check will be performed by counting the tablets returned at each on-site study visit.

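### The SAP compliance formula divides a tablet count by 8, the number of doses, although 18 tablets are prescribed, so full compliance is reported as above 120%

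*SAP*

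**What the plan says.** SAP Section 9.1 takes the tablets dispensed, subtracts the tablets returned, and divides by a constant: "number of tablets returned) / 8 x 100". The result is "summarized as number and percentage of subjects receiving <80%, 80%-120%, and >120% of prescribed study treatment".

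Protocol Section 6.2 gives the regimen in tablets: "a loading dose of 160 mg (consisting of four 40 mg tablets) in the clinic on Day 1 (Week 1"), then "80 mg (consisting of two 40 mg tablets) once weekly (Weeks 2 to 8) thereafter". Table 1 of the protocol puts placebo on the same schedule, so the tablet count is the same in both arms.

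Supply is split over two bottles (Protocol Appendix A, Table 8, footnote n). One "will remain in the clinic for onsite subject dosing" on Days 1, 8 and 29. For the other: "A second bottle will be dispensed to the subject at Day 8 to take home for at-home dosing", on Days 15, 22, 36, 43 and 50. The SAP does not say whether tablets dispensed means both bottles or only the second. Neither document gives a rule for converting tablets to doses.

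**The concern.** The numerator and the divisor are in different units. The constant 8 agrees with the number of weekly doses but not with the number of tablets prescribed, and the categories are labelled as percentages of prescribed treatment. If the formula is programmed as written, subjects who followed the protocol exactly are reported as having received more than 120% of their treatment. Protocol Section 6.8 treats any amount above the specified dose as an overdose, so such a table also invites a false safety reading.

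With both bottles counted the error runs the other way as well: a subject who took less than half of the regimen can appear in the 80%-120% category. This is the only compliance summary in the SAP. The primary estimand follows a treatment policy strategy, under which poor adherence can dilute the estimated effect, so readers of a proof-of-concept result need this table to be right.

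**Working it through.** **Inputs**

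- Divisor: 8 (SAP 9.1).
- Category limits: 80% and 120% (SAP 9.1).
- Tablets per dose: 4 on Day 1, 2 at each later dose (Protocol 6.2).
- Dosing days: 1, 8 and 29 in clinic; 15, 22, 36, 43 and 50 at home (Protocol 6.2; Table 8, footnote n).

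**Where 8 can come from**

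- Doses: 3 + 5 = 8. The divisor matches.
- All tablets: 4 + 7 x 2 = 18. No match.
- Take-home tablets: 5 x 2 = 10. No match.
- Clinic-bottle tablets: 4 + 2 + 2 = 8. This matches, but it leaves out all five at-home doses.

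**Score at full compliance**

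- Both bottles: 18/8 x 100 = 225%, in >120%.
- Take-home bottle only: 10/8 x 100 = 125%, in >120%.

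The number of tablets packed per bottle is not stated, but it does not matter here. For a fully compliant subject, dispensed minus returned equals tablets taken.

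**Both bottles, whole doses taken in order**

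| Doses | Tablets | Tablets/8 | Category as written | Tablets/18 | Category against 18 |
|---|---|---|---|---|---|
| 1 | 4 | 50% | <80% | 22% | <80% |
| 2 | 6 | 75% | <80% | 33% | <80% |
| 3 | 8 | 100% | 80%-120% | 44% | <80% |
| 4 | 10 | 125% | >120% | 56% | <80% |
| 5 | 12 | 150% | >120% | 67% | <80% |
| 6 | 14 | 175% | >120% | 78% | <80% |
| 7 | 16 | 200% | >120% | 89% | 80%-120% |
| 8 | 18 | 225% | >120% | 100% | 80%-120% |

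Six of the eight rows are misclassified; only 1 and 2 doses are placed correctly.

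In single tablets, the limits as written are 0.8 x 8 = 6.4 and 1.2 x 8 = 9.6. The 80%-120% category therefore holds 7 to 9 tablets, which is 7/18 = 39% to 9/18 = 50% of the regimen.

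**Take-home bottle only**

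- 5 of 5 doses: 10/8 = 125% against 10/10 = 100%. Wrong category.
- 4 of 5 doses: 8/8 = 100% against 8/10 = 80%. Same category.
- 3 of 5 doses: 6/8 = 75% against 6/10 = 60%. Same category.

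Under this reading the one wrong category among these is the fully compliant subject.

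**Check of the proposed replacements**

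- Divisor 18: the limits are 0.8 x 18 = 14.4 and 1.2 x 18 = 21.6 tablets, so 7 or 8 whole doses (16 or 18 tablets) fall in 80%-120%.
- Doses over 8: 7/8 = 87.5% and 8/8 = 100% fall in 80%-120%; 6/8 = 75% falls in <80%.

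When doses are taken in order, the two versions agree at every count from 1 to 8.

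**The case against.** - **The origin of 8 is an inference.** The SAP does not say that 8 stands for doses, and the clinic bottle also accounts for 8 prescribed tablets. That is true, but a clinic-bottle reading is not stated and would measure nothing about the at-home doses. If doses were meant, the formula still says tablets.
- **A digit may have been lost.** An 18 that lost its first digit would remove the point, so the divisor is worth a glance at the approved file. The sentence shows no sign of damage, and 8 has an obvious source in the dose count.
- **The documents lean towards the take-home reading.** Footnote n sends the first bottle to the site and the second to the subject, and Protocol 6.5 speaks of what subjects bring back. On the other hand, Table 8 marks dispensing on both Day 1 and Day 8. The question is open. The six-of-eight result needs both bottles; the misclassification of full compliance does not.
- **The benchmark is assumed.** Measuring early stoppers against 18 tablets presumes that prescribed means the full regimen rather than the amount due up to discontinuation. The fixed divisor suggests the full regimen but does not say so. This affects the labels for partial dosing, not those for complete dosing.
- **The consequence is small.** Exposure duration (SAP 9.1) and treatment discontinuation (SAP 6.1) are tabulated separately, and the output review in SAP Section 10 would probably notice nearly every fully dosed subject sitting above 120%. This stands as a limit on weight. It does not make the rule correct.

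**Conclusion.** The concern holds: the formula is wrong as written. A fully compliant subject in either arm scores 225% or 125%, depending on which bottles are counted, and is placed in >120% both ways. With both bottles counted and whole doses taken in order, the category is wrong at six of eight dose counts, and 80%-120% describes subjects who used 39% to 50% of their tablets.

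The damage stops at one descriptive table. The Full Analysis Set is defined regardless of compliance (SAP 5.2), the estimand is treatment policy (SAP 7.3.2), and no sensitivity, supplementary or subgroup analysis uses compliance (SAP 7.4.1, 7.4.2, 7.6.7). The correction should be made, but the primary result does not depend on it.

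The full-compliance figures rest only on the protocol's tablet schedule. The partial-compliance figures also assume that the full 18-tablet regimen is the benchmark.

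**What to change.** In SAP Section 9.1, replace the divisor 8 with 18 and state that tablets from both the clinic bottle and the take-home bottle are counted. Alternatively, count doses in both terms: doses taken / 8 x 100%. The two versions can differ only if doses are missed out of order. A subject who missed just the Day 1 dose would score 14/18 = 77.8% against 7/8 = 87.5%, but this should hardly arise because Day 1 is dosed in the clinic.

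If the sponsor meant the take-home bottle alone, the divisor is 10 and the table should be labelled as at-home compliance. In every version, state whether subjects who stop early are measured against the full regimen.

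The cost is one line of SAP text and the matching program line. No other analysis changes, and no dose or clinical rule is touched. Before choosing the 18-tablet version, confirm that the clinic-bottle counts are in the database, because Protocol 6.5 allows them to be kept on a dispensing log or documented in another way. SAP Section 1 commits to settling analysis decisions before database lock and unblinding, so the correction belongs in the SAP text and not only in the program.

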9.2. Prior and Concomitant Medications

Prior medication is defined as any non-study medication taken before the first dose of study treatment.

Concomitant medication is defined as any non-study medication that is started:

- Before the date of first administration of study treatment and ongoing throughout the study or ends on/after the date of first administration of study treatment.
- On/after the date of fist administration of study treatment and is ongoing or ends during the course of study.

Medications with a start date before the first dose of study treatment and an end date after the first dose of study treatment (or ongoing) will be classified as "both prior and concomitant medication".

The number and percentage of patients taking prior and concomitant medications will be tabulated by WHO Drug Dictionary Anatomical Therapeutic Chemical (ATC) Level 3 category or Level 2 if there is not an applicable Level 3 category, and preferred names using the Safety Analysis Set. Subjects will be counted only once for each ATC or preferred name if they have multiple records of the same ATC or preferred name in the database. The table will be sorted alphabetically by ATC class and then, within an ATC class, by preferred names.

Neurocrine Biosciences, Inc. Statistical Analysis Plan Study NBI-1065846-MDD2020 16August2023

9.3. Adverse Events

Adverse events are recorded in the eCRF. Each AE will be coded to SOC and PT using MedDRA.

A treatment-emergent adverse event (TEAE) is an AE that occurs after the initiation of randomized study treatment dosing. Investigators will be asked to respond "Yes" or "No" on the eCRF as to whether the AE started after the subject took the first dose of study drug. An AE with a response of "Yes" will be classified as a TEAE. If the investigator's response is missing, then the treatment emergent status will be derived based on the AE onset date and time relative to the date and time of the subject's first dose of study drug. If the AE onset date and time are unknown, it will be assumed that the AE is a TEAE. If the AE onset time is unknown but the AE onset date is the same date as the first dose of study drug, it will be assumed that the AE is a TEAE.

The frequency tables will include the number and percentage of unique subjects experiencing each event at least once during the study. Unless otherwise specified, summary tables will include events with a start date on or after the date of the first dose of randomized study treatment and up to the last dose of study treatment + 10 days.

Two versions of the primary TEAE frequency tables will be presented by treatment group:

- Frequency of TEAEs by SOC and PT, with SOCs sorted alphabetically and PTs within each SOC sorted by decreasing frequency (number of unique subjects) in the active treatment group.
- Frequency of TEAEs by PT, with PT sorted by decreasing frequency (number of unique subjects) in the active treatment group.

Summary tables of severe TEAEs will be presented by treatment group. The number and percentage of subjects with a severe TEAE will be presented by PT within SOC (presented in the same method as the primary TEAE table). The first line of the table will display the number and percentage of subjects with at least one severe TEAE.

An AE overview summary table will be provided which summarizes the number and percentage of subjects with any TEAE, any TEAE leading to study treatment discontinuation, any serious TEAE, and any TEAE leading to death. The summary table will also include the maximum TEAE severity (mild, moderate, severe) reported for each subject.

In addition, tables will be provided for non-treatment emergent AEs (AE start dates after last dose date +10 days) separately. These tables will be summarized by treatment group and presented by PT within SOC, with SOCs sorted alphabetically and PTs within each SOC sorted by decreasing frequency (number of unique subjects) in the active group.

9.3.1. Adverse Events Leading to Discontinuation of Study Treatment

Summary tables of TEAEs leading to discontinuation of study treatment will be presented by treatment group. The number and percentage of subjects with a TEAE leading to study treatment discontinuation will be presented by PT within SOC (presented in the same method as the primary TEAE table). More than one AE can contribute to study treatment discontinuation per

Neurocrine Biosciences, Inc. Statistical Analysis Plan Study NBI-1065846-MDD2020 16August2023

subject. The first line of the table will display the number and percentage of subjects with at least one TEAE leading to study treatment discontinuation.

A listing of TEAEs leading to study treatment discontinuation will be provided which includes subject ID, treatment group, last treatment received prior to the onset time of the TEAE(s) leading to discontinuation, study day of the discontinuation, and other relevant information from the AE eCRF. Note that "last treatment received prior to the onset time of the TEAE[s] leading to discontinuation" reflects the actual dose level received prior to the AE.

9.3.2. Deaths and Other Serious Adverse Events

Summary tables of Treatment-emergent SAEs and deaths will be presented by treatment group. The tables will include the frequency of SAEs presented by PT within SOC (presented in the same method as the primary TEAE table).

Separate listings of SAEs and fatal TEAEs will also be provided. Each listing will include subject ID, treatment group, last treatment received prior to the onset time of the SAE or fatal TEAE, study day of the SAE or fatal TEAE, and any additional relevant information from the AE eCRE.

9.4. Laboratory Safety Parameters

The hematology and clinical chemistry will be summarized with descriptive statistics by treatment at baseline and at each scheduled postbaseline visit through follow-up visit (Day 106). Both observed values and changes from baseline will be summarized by treatment group.

Shift tables from baseline to Day 57 will be presented for selected clinical laboratory variables based on the reference range-based categories of "Low," "Normal," or "High." A clinical laboratory variable value will be assigned to one of these three categories according to the reference ranges provided by the central clinical laboratory. The shift table will have rows reflecting the reference range category at baseline, and columns reflecting the reference range category on Day 57. A "Total" row and "Total" column will also be included. The number of subjects in each shift category will be displayed in the table.

The shift table will be presented by treatment group for the following clinical laboratory variables:

- aspartate aminotransferase (AST),
- alanine aminotransferase (ALT),
- alkaline phosphatase (ALP),
- gamma-glutamyl transferase (GGT),
- total bilirubin,
- creatine kinase,
- creatinine,
- blood urea nitrogen (BUN),
- white blood cell count,

Neurocrine Biosciences, Inc. Statistical Analysis Plan Study NBI-1065846-MDD2020 16August2023

- absolute neutrophil count,
- hemoglobin,
- platelet count,

Repeat clinical laboratory samples may be collected at any time during this study due to either missing or abnormal results. The general rule for summarizing these data is to include the original sample results in summary tables. Exceptions to this rule is that if there are missing results from the original lab samples at screening, the results of a repeat screening sample will be substituted for the missing results in summary tables.

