2.2. Benefit/Risk Assessment for NBI-1065846

NBI-1065846 is a potential first-in-class drug; therefore, there are no known class effects. The GPR139 receptor is present in other species, including rats, dogs, and monkeys (NHRPR.org). Cholestatic liver injury was species-specific and observed in the 13-week no observed adverse effect level (NOAEL) toxicity study in dogs, but not in rats or monkeys. The NOAEL was 30 mg/kg/day for both male and female dogs and attributed to hepatic cholestasis and renal tubule degeneration considered secondary to hepatic changes at 60 mg/kg/day, including elevated alanine aminotransferase (ALT), aspartate aminotransferase (AST), bile acids, blood urea nitrogen, creatinine, gamma-glutamyl transferase (GGT), phosphorus, and total bilirubin (TBILI). These findings were monitorable and partially reversible. In this study, monitoring for hepatobiliary injury includes elevation of liver enzymes (eg, ALT, AST, alkaline phosphatase [ALP], GGT, 5'-nucleotidase, and TBILI), physical examinations, and monitoring of treatment-emergent adverse events (TEAEs). Additional assessments may be completed as clinically indicated.

In clinical studies, including the first in human (FIH) Study TAK-041-1001 and Study TAK-041-1002, there were no reported deaths, serious adverse events (SAEs), adverse events (AEs) leading to study treatment or study visit discontinuations, other significant AEs, clinically meaningful safety laboratory results (including ALP, ALT, AST, GGT, 5'-nucleotidase, TBILI), clinically significant physical examination results, vital signs, and/or electrocardiogram (ECG) results.

Although suicidality was not reported in subjects administered NBI-1065846 in the clinical development program, subjects at an imminent risk of suicide per the Columbia-Suicide Severity Rating Scale (C-SSRS) or according to the investigator's clinical judgment will be excluded from this study. Subjects will be assessed for any signs of suicidal ideation or behaviors, and appropriate psychiatric interventions or other precautions will be instituted, if warranted.

Additional information about the benefits and risks of NBI-1065846 is provided in the Investigator's Brochure.

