8.1. Discontinuation of Study Treatment

If a subject prematurely discontinues study treatment, the investigator will record the reason for discontinuation on the relevant eCRF. Data for any outcome measures, particularly the primary and secondary endpoints, as well as safety follow-up, are important to collect. Subjects will not be automatically withdrawn from the study and should continue participation in the study, regardless of study treatment compliance, unless consent for study participation has been withdrawn. For any subsequent study visits after study treatment is prematurely discontinued, subjects should have 1 final PK sample collected (ie, subsequent PK samples are not required); however, subjects should continue with study assessments at the study site or with virtual visits.

If medically indicated, treatment with medication listed under Section 7.1 is no longer prohibited after study treatment discontinuation.

Reasons for discontinuation from study treatment include but are not limited to:

- Withdrawal by subject
- Death
- Lost to follow-up

- Site termination by the Sponsor
- Study termination by the Sponsor
- AE
- Pregnancy
- Lack of efficacy
- Protocol deviation
- Investigator decision
- Sponsor decision

The investigator must discontinue study treatment if the subject experiences any of the following:

- If the type, frequency, or severity of any AE becomes unacceptable/intolerable
- If the subject is unable to tolerate the lowest allowable dose (80 mg or placebo)
- QTcF of >500 msec (cardiologist verified) on any ECG tracing
- If the subject is confirmed to be pregnant
- Withdrawal of consent for study treatment administration by subject
- If the subject exhibits suicidal behavior, or suicidal ideation of type 4 (active suicidal ideation with some intent to act, without specific plan) or type 5 (active suicidal ideation with specific plan and intent) based on the C-SSRS or according to the investigator's clinical judgement
- Study treatment should be discontinued with appropriate clinical follow-up (including repeat laboratory tests) until a subject's laboratory profile has returned to normal/baseline status), if any of the following occur (see Appendix D for additional detail):
 - ALT or AST $>8 \times ULN$, or
 - ALT or AST >5×ULN and persists for more than 2 weeks, or
 - ALT or AST >3×ULN in conjunction with elevated total bilirubin >2×ULN or INR >1.5

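### SAP 9.4 has no worst-value or ULN-multiple liver summary to match the protocol's liver stopping criteria, and its one categorical table is nearly empty under the SAP's own visit windows

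*SAP*

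**What the plan says.** **Protocol.** Section 2.2 reports cholestatic liver injury in dogs and says that in this study "monitoring for hepatobiliary injury includes elevation of liver enzymes", naming ALT, AST, ALP, GGT, 5'-nucleotidase and total bilirubin. Section 8.1 introduces the liver criteria with "Study treatment should be discontinued with appropriate clinical follow-up" and then lists ULN multiples, some of them combined criteria. Appendix D repeats them and adds thresholds for notifying the medical monitor and a retesting schedule. Section 9.3.5 places 5'-nucleotidase in the chemistry panel. Table 8 schedules postbaseline laboratory tests on Days 8, 29, 57, 78 and 106.

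**SAP 9.4.** Hematology and chemistry are summarised at baseline and at every scheduled visit to Day 106: "Both observed values and changes from baseline will be summarized by treatment group". The one categorical output is then given: "Shift tables from baseline to Day 57 will be presented for selected clinical laboratory variables". On the bands: "A clinical laboratory variable value will be assigned to one of these three categories according to the reference ranges provided by the central clinical laboratory". Twelve entries make up the list that follows "The shift table will be presented by treatment group for the following clinical laboratory variables". Its liver tests are AST, ALT, ALP, GGT and total bilirubin. For repeat samples, the original result enters the summary tables, with an exception only for results missing at screening.

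**SAP 5.6.** Safety visits, including unscheduled and repeated ones, are re-mapped by Table 2. If several values fall in one window, the one closest to the target day is used.

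**The concern.** The liver is the organ for which the protocol sets the most detailed stopping rules, and a reader of the study report will ask how many subjects in each arm met them. The SAP does not plan an output that answers this. High does not separate a value just above the limit from one above 8×ULN. One stopping analyte is missing from the shift list. The table looks at one time point rather than at each subject's worst value.

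The safety conclusion of a proof-of-concept trial with about 44 subjects per arm is at stake. A few threshold crossings in the active arm would matter for further development, and by-visit means will hardly move.

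**Working it through.** The plan states no figure on this point, so there is none to reproduce. The check sets protocol criteria against SAP outputs and then applies the SAP's windows to the visit schedule.

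**1. Stopping criteria against SAP 9.4 outputs**

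| Protocol 8.1 / Appendix D | What SAP 9.4 can show |
|---|---|
| ALT or AST >8×ULN | High; by-visit maximum |
| ALT or AST >5×ULN for over 2 weeks | Nothing on persistence |
| ALT or AST >3×ULN with bilirubin >2×ULN or INR >1.5 | Each chemistry analyte separately; INR belongs to the coagulation panel, which 9.4 does not name |
| ALT or AST >3×ULN with symptoms or eosinophilia | Nothing joint |
| ALP >1.5×ULN with bilirubin >1.5×ULN | Each analyte separately |
| 5'-nucleotidase >2×ULN | By-visit summary only |
| GGT >5×ULN; AST/ALT >3×ULN | High; by-visit maximum |

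No row has a count of subjects over the threshold. The SAP's abbreviation list contains ULN and potentially clinically significant, but no visible analysis uses either.

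**2. The Day 57 column for subjects on schedule**

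Inputs: last scheduled dose Day 50, ±2 days (protocol 6.2), so Days 48 to 52; Day 57 visit ±2 days (Table 8), so Days 55 to 59. SAP Table 2 windows: Day 57 runs from Day 51 to the last dose day; Day 78 from last dose +1 to last dose +42, with target last dose +28.

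- To map to Day 57, the visit day must be no later than the last dose day. The earliest visit is Day 55 and the latest last dose is Day 52, so 0 of 5 × 5 = 25 combinations qualify. For last doses on Days 48 to 50 the window contains no day at all.
- The visit falls between 55 − 52 = 3 and 59 − 48 = 11 days after the last dose, so all 25 map to Day 78.
- There the sample lies 28 − 11 = 17 to 28 − 3 = 25 days from target. The actual Day 78 visit (Days 75 to 81, target Days 76 to 80) lies at most 5 days away. The closest-to-target rule therefore drops the Day 57 sample whenever a Day 78 sample exists, and it is lost from the by-visit summaries too.

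**3. Subjects who stop early**

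Any last dose before Day 51 leaves the Day 57 window without days. With the last dose on Day 29, a Day 57 sample is 57 − 29 = 28 days after it and maps to Day 78. With the last dose on Day 8, it is 57 − 8 = 49 days after and maps to Day 106, which starts at last dose +43. The windows can also overlap. With the last dose on Day 22, a Day 29 sample fits both Day 29 (Days 26 to 36) and Day 78 (Days 23 to 64), and the SAP does not say which applies.

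**4. What a by-visit summary shows**

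Assumed data for one arm of 88/2 = 44 at one visit: 43 subjects at 0.5×ULN and one at 6×ULN. The mean is (43 × 0.5 + 6)/44 = 27.5/44 = 0.625×ULN, the median 0.5 and the maximum 6. The maximum reveals the case. It would be the same 6 if several subjects had crossed 3×ULN, and it does not say whether bilirubin rose in the same subject.

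**5. Repeat samples**

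Appendix D asks for retesting within 48 to 72 hours of a transaminase above 3×ULN, then two or three times weekly if it persists. A peak is thus likely to fall on a repeat or unscheduled sample. The original-sample rule (9.4) and the closest-to-target rule (5.6) can both leave that value out.

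**6. The SAP's own precedent**

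For QTcF, SAP 9.7 takes each subject's highest postbaseline value, including unscheduled visits, and counts subjects above thresholds that include 500 msec, the stopping value in protocol 8.1.

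**The case against.** The best defence is that the SAP does more than the shift table. Chemistry is summarised at each scheduled visit through Day 106, SAP 5.1 includes the maximum in descriptive statistics, and 5'-nucleotidase is in the chemistry panel. A drug-stopping elevation can also surface in the discontinuation reasons (SAP 6.1) and in the table and listing of TEAEs leading to discontinuation (SAP 9.3.1), since protocol 10.1 allows an abnormal laboratory finding to be an adverse event. Protocol 11.5.2 promises only descriptive statistics for selected analytes. Subjects are protected by real-time monitoring, not by an end-of-study table.

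Much of this stands. A reader might infer that a transient or drug-stopping elevation would be invisible in the safety outputs; the documents do not support that. A reader might also infer that a subject stopped at Day 8 or Day 29 would recover off drug and appear as Normal at Day 57. As step 3 shows, Table 2 gives such a subject no Day 57 value at all. That picture could arise only if the table were programmed on nominal visits, which SAP 5.6 does not say.

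The defence does not supply the missing count. The adverse event route depends on how the site records the event: protocol 8.1 names an AE and an abnormal laboratory test separately as causes of stopping, and SAP 9.3.1 covers TEAEs only. A discontinuation reason of AE does not identify the liver.

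**Conclusion.** The concern holds in a limited form. The SAP has no worst-postbaseline, ULN-multiple or combined transaminase and bilirubin summary, although the protocol sets stopping criteria in exactly those terms. The one categorical table omits 5'-nucleotidase. Read literally, its Day 57 column takes none of the 25 on-schedule combinations and excludes early stoppers.

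Elevations are not hidden altogether: by-visit maxima and adverse event or discontinuation outputs can show them. Three things are not shown reliably or at all: how many subjects crossed a threshold, whether ALT or AST rose together with bilirubin, and peaks seen only on repeat or unscheduled samples.

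The window result assumes that Table 2 is programmed as written and that doses and visits stay within their allowed windows. The illustration in step 4 uses assumed values. The efficacy analysis is not affected.

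**What to change.** - **Shift table:** change it to baseline versus worst postbaseline value, using scheduled, unscheduled and repeat samples. State this as an explicit exception to the original-sample rule in 9.4 and the closest-to-target rule in 5.6. Add 5'-nucleotidase.
- **Threshold table and listing:** by arm, count and list the subjects whose highest postbaseline value exceeds each ULN multiple already in protocol Section 8.1 and Appendix D. Include the combined criteria with a stated definition of concurrence, and bring in INR for the criterion that uses it. The listing should carry dates so that persistence can be judged.
- **Visit window:** reconcile the Day 57 safety window in SAP Table 2 with the Day 50 last dose, and say which window applies where two overlap after early stopping.
- **Protocol criteria:** have the sponsor reconcile the overlapping criteria before the categories are fixed. AST/ALT >3×ULN stands in the same lists as >8×ULN, as >5×ULN for over 2 weeks, and as >3×ULN with further conditions. Elsewhere Appendix D answers a value above 3×ULN with retesting and possible discontinuation. Which reading is right is for the sponsor to settle.

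The cost is one changed table, one added table and one listing, all from data already collected, plus the two reconciliations.
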